2.3 Primary Endpoint(s)

Safety:

1. Incidence and severity of AEs and Adverse Events of interest (urinary retention, withdrawal symptoms) over the course of the study. AEs are recorded at visits 2,3,4,5,6 and 7.
2. Adverse Events of special psychiatry interest (nervousness, anxiety, panic attacks, insomnia, aggression, mania, suicidal ideation, development/worsening of depression) over the course of the study
3. Suicidal Adverse Events and Adverse Events suggestive of abuse potential will be analysed, and detailed narratives provided
4. Lab parameters: Haematology and chemistry recorded at visit 1,2,6 and 7. Urinalysis recorded at visit 1 and 2.
5. Absolute change from end of the Screening Placebo Run-In Period in ECG readings and Week 8 (Visit 6). ECG parameters of interest include: ventricular rate, QT interval, corrected QT interval, PR interval, and QRS duration
6. Absolute change from end of the Screening Placebo Run-In Period to each visit in standardised cuff systolic and diastolic blood pressure and radial heart rate

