6.2 Covariate and Subgroups

Safety

Age (under 65, over 65) is used as subgroup for the analysis of treatment emergent adverse event.

Efficacy

The methodology described in the protocol for the efficacy analyses is a mixed model with repeated measures (MMRM). In light of the fact that the efficacy measurements were recorded at visit 2 and visit 6 only, there are no repeated measures. Therefore, the MMRM model described in the protocol cannot be applied to these analyses. The efficacy analyses will be conducted as an analysis of covariance (ANCOVA).

The model will include Baseline values as a covariate and dose and site as factor variables.

Baseline is defined as end of Screening Placebo Run-in for all efficacy analyses (Visit 2).

Exploratory efficacy analysis will be performed based on the baseline severity of incontinence episodes, as defined in section 5.4.2. Patients will be divided in 2 groups according to the median number of incontinence episodes.

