6.7 Safety Analysis

The general objectives of this study are to establish the safety, tolerability and efficacy of litoxetine in men and women who suffer from UI. The primary analyses will focus on safety, describing the adverse events with point estimates and Clopper Pearson 95% confidence intervals. All safety analyses will be conducted on the safety population.

All AEs will be coded using the MedDRA dictionary (version 20.1).

1. Incidence and severity of Treatment Emergent Adverse Events and Treatment Emergent Adverse Events of interest (urinary retention, withdrawal symptoms) over the course of the study.

The Treatment Emergent Adverse Events (TEAEs) and the TEAEs of Interest will be summarised by treatment group. The SOCs and PTs will be used for tabulation. The number of TEAEs/TEAEs of interest and the number and the percentage of patients with at least one AE will be presented by SOC and PT for each treatment group. Within each SOC and PT, the highest severity grade attained will be reported, for AEs with divergent severities.

TEAEs/TEAEs of interest will be described with point estimates and Clopper Pearson 95% confidence intervals.

The analysis of treatment emergent adverse events is the primary safety endpoint, the analysis of TEAEs of interest is considered as part of the secondary safety analysis.

2. Treatment Emergent Adverse Events of special psychiatry interest (nervousness, anxiety, panic attacks, insomnia, aggression, mania, suicidal ideation, development/worsening of depression) over the course of the study

The Treatment Emergent Adverse Events of special psychiatry interest will be summarised by treatment group. The SOCs and PTs will be used for tabulation. The number of AEs and the number and the percentage of patients with at least one AE will be presented by SOC and PT for each treatment group. Within each SOC and PT, the highest severity grade attained will be reported, for AEs with divergent severities.

Adverse events will be described with point estimates and Clopper Pearson 95% confidence intervals.

3. Treatment Emergent Suicidal Adverse Events and Adverse Events suggestive of abuse potential

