5. Absolute change from end of the Screening Placebo Run-In Period in ECG readings and Week 8. ECG parameters of interest include: ventricular rate, QT interval, corrected QT interval, PR interval, and QRS duration

Absolute values and also change from baseline (Screening Placebo Run-In Period) in ECG readings at Week 8 (Visit 6) will be summarised by descriptive statistics.

ECG parameters of interest include:

- a. Ventricular rate
- b. QT interval

- c. Corrected QT interval
- d. PR interval
- e. RR interval
- f. QRS duration.

6. Absolute change from end of the Placebo Run-In Period to each visit in standardised cuff systolic and diastolic blood pressure and radial heart rate

Absolute change from baseline (Visit 2) to each visit (Visits 3, 4, 5 and 6) for Systolic and Diastolic blood pressure will be summarised by treatment group. The average value of 3 recordings will be considered in the analysis.

A t-test will be used to test a difference between arms only for the change of systolic and diastolic blood pressure from Baseline (Visit 2) to Endpoint (Visit 6). Hypothesis testing will be carried out at the alpha = 0.05 level (two-sided) when comparing treatments. P-value and 95% Confidence Interval will be reported. Statistical significance will be declared if the rounded p-value will be less than or equal to 0.05.

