The medical history should include demographic information, urinary and incontinence history (with date of onset), past treatment(s) for incontinence, current co morbidities, relevant past illnesses, surgical

procedures performed within the prior 6 months, all current medications (including those taken within 30 days prior to Screening), and smoking history (including current usage, if applicable).

Past and concomitant diseases will be coded using MedDRA dictionary (version 20.1) and frequency distributions and percentages will be summarised by treatment group for the safety population by SOC and PT.

Counts will be given for both SOC and PT by subject. Subjects experiencing more than one past disease (or concomitant disease) event within a given SOC category will be counted only once within that SOC. Similarly, subjects experiencing more than one past disease (or concomitant disease) event fitting a given PT will be counted only once for that PT.

Summary tabulations for the Safety Population, including the number and percentage of subjects with past and concomitant diseases by SOC and PT, and further categorised by treatment arm will be added.

12-Lead ECG

Actual values and also change from baseline in ECG readings at Visit 2 (baseline), Visit 3, Visit 4, Visit 5, Visit 6 will be summarised by descriptive statistics.

ECG parameters of interest include:

1. Ventricular rate
2. QT interval
3. Corrected QT interval
4. PR interval
5. RR interval
6. QRS duration.

All three measurements for each parameter will be reported. A shift table presenting the number and the percentage of patients in each bivariate category (Baseline to Endpoint) with regards to investigator's interpretation (Normal, Abnormal NCS, Abnormal CS, Not done) will be provided by treatment group.

QT will be corrected for HR using the following formulas:

- Fridericia's correction ($QTc=QT/RR^{0.33}$),
- Bazett's correction ($QTc=QT/RR^{0.5}$)
- Framingham correction ($QTc=QT+0.154(1-RR)$)

Change in QT and QTc for each correction method, will be analysed by central tendency and as categorical analyses. The mean of the QT and HR (obtained in triplicate) will be used.

Central tendency analysis will include:

- Change from baseline (V2) at all time points.
- The change from baseline to Visit 6 in active treatment group will be compared to placebo with a two-sided t-test. The level of significance alpha will be set equal to 5%.
- Results will be reported by 95% CI

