Categorical analysis will be conducted based on predetermined thresholds (Visit 2, Visit 3, Visit 4, Visit 5, Visit 6):

- Number of subjects with $450 < QT \leq 480$ ms, $480 \text{ ms} < QT \leq 500$ ms and $QT > 500$ ms
- Number of subjects with $450 < QTc \leq 480$ ms, $480 \text{ ms} < QTc \leq 500$ ms and $QTc > 500$ ms

- Number of subjects with increase in QT from baseline >30 ms and <= 60 ms, as well as >60 ms
- Number of subjects with increase in average QTc from baseline >30 ms and <= 60 ms, as well as >60 ms

Tabulation of the results will follow Appendix 1, Guide for the analysis and review of QT and QTc Interval data, Health Canada, 2010.

Psychiatric monitoring

Answers of the questionnaires for psychiatric monitoring will be listed.

In particular, answers for the following questionnaires will be reported:

1. Columbia-Suicide Severity Rating Scale (C-SSRS)
2. Beck Depression Inventory-II (BDI-II)
3. Beck Anxiety Inventory (BAI)
4. Pittsburgh Sleep Quality Index (PSQI)

For the Columbia-Suicide Severity Rating Scale (C-SSRS), summary tables will be used to present the results at visit 1, visit 2, visit 3, visit 4, visit 5, telephone contact at day 42, visit 6 and visit 7. Patients will be classified into 3 categories of subjects with suicidal behaviour, suicidal ideation and suicidal ideation or behaviour according to the Columbia Scoring and Data Analysis Guide (see Appendix 2). Subcategories will also be included. A subject has a suicidal ideation if she/he reports “yes” answer at any time during treatment to any one of the five suicidal ideation questions (Categories 1-5) on the C-SSRS; a suicidal behaviour if there is a “yes” answer to any one of the five suicidal behaviour questions (Categories 6-10); a suicidal ideation or behaviour is the subject has either suicidal ideation or behaviour.

The Suicidal Ideation Score corresponds to the ‘Most severe Ideation’ score reported in the eCRF and it will be presented as listings. A missing suicidal ideation score means no ideation is present. A shift table will be provided to demonstrate changes in C-SSRS categories from Baseline to Visit 6.

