$$\Delta = \exp\left(\log\left(\frac{\%UIE_{Litoxetine}}{\%UIE_{Placebo}}\right)\right) = \frac{\%UIE_{Litoxetine}}{\%UIE_{Placebo}}$$

$\%UIE_i$ is the ratio of the total number of urinary incontinence episodes in a week at endpoint (Visit 6) ($UIE_{i,end}$) to the total number of urinary incontinence episodes in a week at baseline ($UIE_{i,base}$) for arm i , with i equal to Litoxetine or Placebo.

An ANCOVA will be performed to compare δ to 0; the test will provide an appropriate p-value with a significance level alpha equal to 0.05. This p-value will be computing the probability of observing a difference among arms.

Numbers of incontinence episodes equal to 0 (not missing) will be imputed as 0.4 to allow for the log transformation.

2. Absolute change from end of the Screening Placebo Run-In Period to Week 8 in the number of incontinence episodes/24 hours (daily average)

The analysis planned is an analysis of covariance model (ANCOVA). Absolute change in the total number of incontinence episodes/24 hours is the response variable. The factor variables will be dose and centre. The covariate will be end of the Screening Placebo Run-In Period episodes of incontinence.

Number of incontinence episodes/24 hours will be computed as Total Number of incontinence episodes recorded during the 7-day period and entered in the eCRF divided by 7, as defined in Section 5.4.

The hypothesis test being conducted is as follows:

$$H_0: \Delta UIE_{Litoxetine} - \Delta UIE_{Placebo} = 0$$
$$H_1: \Delta UIE_{Litoxetine} - \Delta UIE_{Placebo} \neq 0$$

Where ΔUIE_i is the absolute change, for subjects in arm i , in the number of incontinence episodes/24 hours as defined above from baseline ($UIE_{i,base}$) to the final measurement ($UIE_{i,end}$):

$$\Delta UIE_i = UIE_{i,end} - UIE_{i,base}.$$

Where i goes from 1 to 2 and it represents the 2 arms: Litoxetine and Placebo.

3. Proportion of subjects who become continent at Week 8

A subject is defined as continent if s/he has no incontinence episodes at Visit 6 (Week 8). Frequencies will be used to describe the proportion of subjects who are continent at Week 8. The proportion will be computed on the total number of subjects for each arm at baseline. The category Missing will be included in the analysis, to consider subjects who do not attend the visit or who have missing values for that visit.

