Differences between groups will be evaluated using Chi-square test or Fisher's exact test (if more than 20% of the cells in a contingency table have counts less than 5).

4. Change from end of the Screening Placebo Run-In Period to Week 8 in the number of incontinence pads used per week

The analysis planned is an analysis of covariance model (ANCOVA). Absolute change in the number of incontinence pads used per week is the response variable. The factor variables will be dose and centre. The covariate will be the number of pads used at the end of the Screening Placebo Run-In Period.

Number of incontinence pads used per week will be derived for the eCRF, as defined in Section 5.4.

The hypothesis test being conducted is as follows:

$$\begin{aligned} H_0: \Delta \text{Pads}_{\text{Litoxetin}} - \Delta \text{Pads}_{\text{Placebo}} &= 0 \\ H_1: \Delta \text{Pads}_{\text{Litoxetin}} - \Delta \text{Pads}_{\text{Placebo}} &\neq 0 \end{aligned}$$

Where ΔPads_i is the absolute change, for subjects in arm i , in the number of incontinence pads used per week from baseline ($\text{Pads}_{i,\text{base}}$) to the final measurement ($\text{Pads}_{i,\text{end}}$):

$$\Delta \text{Pads}_i = \text{Pads}_{i,\text{end}} - \text{Pads}_{i,\text{base}}.$$

Where i goes from 1 to 2 and it represents the 2 arms: Litoxetin and Placebo.

5. Percentage change from end of the Screening Placebo Run-In Period to Week 8 in the number of nocturia episodes in a week

The analysis planned is an analysis of covariance model (ANCOVA). Percentage change in the total number of nocturia episodes in a week is the response variable. The factor variables will be dose and centre. The covariate will be end of the Screening Placebo Run-In Period episodes of incontinence.

The number of nocturia episodes in a week is the total number of nocturia episodes recorded over the 7-day period and entered in the eCRF, as defined in Section 5.4.

The analysis will be carried out as described in section 6.9 point 1.

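### Blood pressure and QT/QTc changes are compared by t-test without the Visit 2 value as a covariate, which gives up some precision

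*SAP*

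**What the plan says.** Two sets of between-arm safety tests are involved.

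- **Blood pressure (SAP 6.7, item 6):** "A t-test will be used to test a difference between arms only for the change of systolic and diastolic blood pressure", from Visit 2 to Visit 6, two-sided at 0.05, with a p-value and 95% confidence interval.
- **QT and QTc (SAP 6.8, 12-Lead ECG):** "The change from baseline to Visit 6 in active treatment group will be compared to placebo with a two-sided t-test", at the 5% level, with 95% intervals. This covers uncorrected QT and three heart-rate corrections.

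Neither text names a covariate. For efficacy the SAP does otherwise. SAP 6.2, under its Efficacy heading, says: "The model will include Baseline values as a covariate and dose and site as factor variables". SAP 6.9 item 2 applies this to a simple change: "Absolute change in the total number of incontinence episodes/24 hours is the response variable", with the run-in episodes as covariate. Item 4 does so for pads: "The covariate will be the number of pads used at the end of the Screening Placebo Run-In Period". SAP 5.5 sets Visit 2 as the baseline for all safety variables, so the covariate is already collected.

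On importance, item 6 of the primary endpoint list in SAP 2.3 is the change "to each visit in standardised cuff systolic and diastolic blood pressure and radial heart rate". SAP 6.7 item 1, however, narrows the primary role: "The analysis of treatment emergent adverse events is the primary safety endpoint". The QT/QTc test belongs to the additional safety analyses and sits beside counts above fixed limits: "Categorical analysis will be conducted based on predetermined thresholds".

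**The concern.** A change between the same two visits gets a baseline covariate when it measures efficacy and none when it measures safety, and no reason is given. The change score does use the baseline, but by subtracting it with a fixed slope of 1. ANCOVA estimates the slope instead. When the true slope is below 1, subtraction over-corrects: it leaves extra noise in the estimate, and a chance difference between arms at Visit 2 pushes the result in the opposite direction.

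These are the only between-arm tests planned for blood pressure and for mean QT/QTc change, in a small 2:1 trial whose first objective is safety. At stake is the width of the reported intervals. Neither bias nor the type I error rate is in question.

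**Working it through.** **Inputs from the documents.** About 78 randomised 2:1, so 52:26; 60 evaluable, so 40:20 (SAP 3.1). Two-sided alpha 0.05. Safety baseline at Visit 2 (SAP 5.5). Mean blood pressure at entry no higher than 140/90 mmHg (Protocol 4.1, criterion 8).

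**Not in the documents.** The SDs and the correlation ρ between the Visit 2 and Visit 6 values. I assume ρ = 0.5, 0.7 and 0.9.

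**The plan's own precision figure.** Protocol 8.10 gives ±14% for an event rate in the treatment arm. With 26 events in 52 subjects the Clopper-Pearson interval is 35.8% to 64.2%, a half-width of 14.2%, so the figure reproduces for the randomised litoxetine arm. No figure is given for the blood pressure or QT/QTc comparisons.

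**Equal variances, large-sample form.** With SD s at both visits, the variance per subject is:

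- t-test on change: 2s²(1 − ρ)
- ANCOVA: s²(1 − ρ²)
- ratio ANCOVA / t-test: (1 + ρ)/2 = 0.75, 0.85, 0.95

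The t-test interval is therefore 1/√0.75 = 1.155, 1/√0.85 = 1.085 and 1/√0.95 = 1.026 times as wide. In sample-size terms the loss equals 33%, 18% and 5% more subjects (1/0.75, 1/0.85, 1/0.95).

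**Small-sample form.** ANCOVA loses one degree of freedom and its variance carries a factor of 1 + 1/(N − 4). At 52:26, √(1/52 + 1/26) = 0.240. At ρ = 0.5 the half-widths in SD units are 0.478 (t-test) and 0.417 (ANCOVA), a ratio of 1.147.

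**Simulation.** 8,000 trials per cell with no true effect; the entries are mean 95% interval width, t-test over ANCOVA. The capped rows cut the baseline at an assumed +1 SD to mimic the blood pressure limit; ρ there is the correlation before the cut.

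| Setting | ρ = 0.5 | ρ = 0.7 | ρ = 0.9 |
|---|---|---|---|
| 52:26, equal variances | 1.147 | 1.077 | 1.019 |
| 40:20, equal variances | 1.142 | 1.074 | 1.016 |
| 52:26, baseline capped | 1.093 | 1.046 | 1.009 |
| 40:20, baseline capped | 1.088 | 1.045 | 1.007 |

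Coverage of both methods lay between 0.946 and 0.957. A separate simulation at 40:20 (20,000 trials; systolic mean 128 and SD 14 assumed, cut at 140) gave standard-error ratios of 1.084, 1.039 and 1.006, close to the last row.

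**Unequal SDs.** If the baseline SD is k times the Visit 6 SD, the variance ratio ANCOVA / t-test is (1 − ρ²)/(1 + k² − 2ρk). For k = 0.8:

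- ρ = 0.5: 0.75/0.84 = 0.893, so the t-test interval is 6% wider
- ρ = 0.7: 0.51/0.52 = 0.981, so 1% wider
- ρ = 0.8: 0.36/0.36 = 1.000, so no gain

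The denominator is smallest at k = ρ, where it equals the numerator. Apart from the cost of estimating the slope, ANCOVA is therefore never less precise than the change score.

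**Chance imbalance.** At 52:26 one standard error of the Visit 2 difference is D = 0.24 SD. With equal variances the change-score estimate then moves by −(1 − ρ)D, which is −0.12, −0.07 and −0.02 SD at ρ = 0.5, 0.7 and 0.9.

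**The case against.** The strongest reply is that this is a choice between two valid methods. The stated endpoint is the change, and a t-test on the change estimates it without bias and with correct coverage. The Protocol (8.7.2) promises only summaries of vital signs, so the t-test is already an addition. The efficacy covariate was carried over from the Protocol's efficacy model, which also has centre as a factor in the Protocol synopsis; the remedy here takes only part of that model. No margin, stopping rule or sample size depends on these tests.

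The gain for blood pressure may also be smaller than the equal-variance figures suggest. The entry cap narrows the baseline spread. Protocol 6.1.4 asks for three vital-sign readings at the randomisation visit only, and SAP 6.7 averages three recordings without saying at which visits. If Visit 6 is a single reading, a simulation at 40:20 with the cap, and within-visit error assumed at 10%, 20% or 30% of single-reading variance, puts the excess width at 7%, 6% or 4% for ρ = 0.5 and 3%, 1.4% or 0.1% for ρ = 0.7. In the last case ANCOVA was the narrower in only 42% of trials.

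All of this stands, and it limits the importance of the point. It does not give a reason to prefer the t-test: at worst ANCOVA costs one degree of freedom, and the estimand is unchanged. The difference between safety and efficacy variables may explain how the two models arose, but it does not make a fixed slope of 1 the better choice.

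**Conclusion.** The point holds, as an optional improvement. Both sets of safety t-tests forgo a covariate that the trial already collects and that the SAP uses for its efficacy changes.

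At 52:26, the t-test intervals are wider on average by about 15%, 8% or 2% (ρ = 0.5, 0.7 or 0.9) with equal variances. That is the more relevant case for QT/QTc, which has no numeric entry cap. For blood pressure with the assumed cap the figures are about 9%, 5% or 1%. The loss approaches nil at high correlation, or when the baseline SD is small relative to Visit 6.

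These sizes rest on assumed correlations and SD ratios, so only the range can be defended. The adverse-event, threshold and shift-table analyses are not affected.

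**What to change.** In SAP 6.7 item 6, and in the QT/QTc central-tendency analysis of SAP 6.8, replace the t-test by ANCOVA of the change (or of the Visit 6 value) on treatment arm, with the Visit 2 value of the same variable as covariate. Report the adjusted difference with its 95% confidence interval. Both forms of the response give the same treatment estimate, so the endpoint remains the change from end of run-in. SAP 6.7 should also say at which visits three blood pressure recordings are averaged.

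A repeated-measures model over Visits 3 to 6 is possible but not needed. Its gain was not quantified, and Visits 3 and 4 close the 10 mg and 20 mg weeks.

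The cost is wording in two places, one model term and one degree of freedom. No new data are needed, and the Protocol does not prescribe the t-test, so it need not change.

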6.8 Additional Safety Analyses

Adverse Events

The number of treatment-emergent AEs, non-TEAEs, AEs occurring during follow-up or following discontinuation, AEs leading to death, AEs leading to discontinuation and SAEs, and the number and the percentage of patients experiencing those events, will be summarised by treatment group. Differences between groups will be evaluated using Chi-square test or Fisher's exact test (if more than 20% of the cells in a contingency table have counts less than 5).

The following adverse events will be specifically summarized by treatment:

1. TEAEs of Special Interest include urinary retention, psychiatric adverse events (nervousness, anxiety, panic attacks, insomnia, aggression, mania, suicidal ideation, development/worsening of depression) and withdrawal symptoms
2. Treatment Emergent Suicidal Adverse Events and Adverse Events suggestive of abuse potential
3. SAEs
4. TEAEs
5. Non-TEAEs
6. AEs/SAEs which occurred during the 30-day Follow-up Period or following discontinuation

The SOCs and PTs will be used for tabulation. The number of AEs and the number and the percentage of patients with at least one AE will be presented by SOC and PT for each treatment group. Within each SOC and PT, the highest severity grade attained will be reported, for AEs with divergent severities.

A comparison of treatment-emergent AE rates between lítoxetine and placebo will be performed using an exact logistic regression model with the treatment-emergent AE ("1"=At least one treatment-emergent AE occurred for the patient; "0"=otherwise) as dependent variable and lítoxetine dose as fixed effects. The probability modelled will be treatment-emergent AE="1".

The number of patients and the number of patients considered in the model will be provided. The exact odds ratio of the fixed effects will be calculated as the number of patients with/without AEs in all arms. If the omnibus test is significant, comparisons between arms will be tested individually, with the relative 95% CI and p-value.

The same model will be repeated by considering SAE ("1"=At least one SAE occurred for the patient; "0"=otherwise) as dependent variable.

AEs leading to study drug discontinuation and AEs leading to death will be presented in the listings only.

SAEs will be listed and summarised in a table, including a description of each event, the time to onset, the severity, and the relationship to trial drug.

All AEs (excluding SAEs) will be listed, and their time to onset, frequency, severity, and relationship to the trial drug will be tabulated by treatment. Non-TEAEs will be summarised separately from TEAEs.

A subgroup analysis of TEAEs will be presented. Subjects will be divided according to age (under 65, over 65). The SOCs and PTs will be used for tabulation. The number of TEAEs and the number and the percentage of patients with at least one TEAE will be presented by SOC and PT for each treatment group and according to the patient's age.

An additional analysis will explore the TEAEs that lead to study drug reduction. Results will be presented as listings as well as with means of descriptive statistics.

Withdrawals

Premature withdrawals from the trial will be displayed and summarised by primary reason and treatment.

Physical examination

Abnormal physical examination findings will be summarised. For each physical examination a shift table presenting the number and the percentage of patients in each bivariate category (baseline versus Week 8 (Visit 6)) with regards to investigator's interpretation (Normal, Abnormal NCS, Abnormal CS, Not done) will be provided by treatment group.

The other results of targeted physical examination will be only listed.

Concomitant Medications

Concomitant medications will be presented in summary tables and listings. They will be classified according to whether they were taken before the trial (and ongoing into the trial), or started during the trial period. A medication will be defined as concomitant if taken after the date of informed consent.

The following information will be reported for each concomitant medication: generic name, route of administration, start date, stop date, frequency, dosage, and indication.

Prior Medications

Prior medications will be presented in summary tables and listings. Medications will be classified as prior medications if taken before the date of informed consent.

Vital signs

Vital signs will be summarised by treatment group at each visit (Baseline, Visit 3, Visit 4, Visit 5, Visit 6) by means of descriptive statistics and listed by subject.

Parameters collected include:

1. Heart Rate (bpm)
2. Body Temperature (Degree Centigrade)

An additional analysis will be performed also on radial heart rate. The actual change from baseline to each visit (Visit 3, Visit 4, Visit 5, Visit 6) in radial heart rate will be computed.

Past and Concomitant Diseases

The medical history should include demographic information, urinary and incontinence history (with date of onset), past treatment(s) for incontinence, current co morbidities, relevant past illnesses, surgical

procedures performed within the prior 6 months, all current medications (including those taken within 30 days prior to Screening), and smoking history (including current usage, if applicable).

Past and concomitant diseases will be coded using MedDRA dictionary (version 20.1) and frequency distributions and percentages will be summarised by treatment group for the safety population by SOC and PT.

Counts will be given for both SOC and PT by subject. Subjects experiencing more than one past disease (or concomitant disease) event within a given SOC category will be counted only once within that SOC. Similarly, subjects experiencing more than one past disease (or concomitant disease) event fitting a given PT will be counted only once for that PT.

Summary tabulations for the Safety Population, including the number and percentage of subjects with past and concomitant diseases by SOC and PT, and further categorised by treatment arm will be added.

12-Lead ECG

Actual values and also change from baseline in ECG readings at Visit 2 (baseline), Visit 3, Visit 4, Visit 5, Visit 6 will be summarised by descriptive statistics.

ECG parameters of interest include:

1. Ventricular rate
2. QT interval
3. Corrected QT interval
4. PR interval
5. RR interval
6. QRS duration.

All three measurements for each parameter will be reported. A shift table presenting the number and the percentage of patients in each bivariate category (Baseline to Endpoint) with regards to investigator's interpretation (Normal, Abnormal NCS, Abnormal CS, Not done) will be provided by treatment group.

QT will be corrected for HR using the following formulas:

- Fridericia's correction ($QTc=QT/RR^{0.33}$),
- Bazett's correction ($QTc=QT/RR^{0.5}$)
- Framingham correction ($QTc=QT+0.154(1-RR)$)

Change in QT and QTc for each correction method, will be analysed by central tendency and as categorical analyses. The mean of the QT and HR (obtained in triplicate) will be used.

Central tendency analysis will include:

- Change from baseline (V2) at all time points.
- The change from baseline to Visit 6 in active treatment group will be compared to placebo with a two-sided t-test. The level of significance alpha will be set equal to 5%.
- Results will be reported by 95% CI

Categorical analysis will be conducted based on predetermined thresholds (Visit 2, Visit 3, Visit 4, Visit 5, Visit 6):

- Number of subjects with $450 < QT \leq 480$ ms, $480 \text{ ms} < QT \leq 500$ ms and $QT > 500$ ms
- Number of subjects with $450 < QTc \leq 480$ ms, $480 \text{ ms} < QTc \leq 500$ ms and $QTc > 500$ ms

- Number of subjects with increase in QT from baseline >30 ms and <= 60 ms, as well as >60 ms
- Number of subjects with increase in average QTc from baseline >30 ms and <= 60 ms, as well as >60 ms

Tabulation of the results will follow Appendix 1, Guide for the analysis and review of QT and QTc Interval data, Health Canada, 2010.

Psychiatric monitoring

Answers of the questionnaires for psychiatric monitoring will be listed.

In particular, answers for the following questionnaires will be reported:

1. Columbia-Suicide Severity Rating Scale (C-SSRS)
2. Beck Depression Inventory-II (BDI-II)
3. Beck Anxiety Inventory (BAI)
4. Pittsburgh Sleep Quality Index (PSQI)

For the Columbia-Suicide Severity Rating Scale (C-SSRS), summary tables will be used to present the results at visit 1, visit 2, visit 3, visit 4, visit 5, telephone contact at day 42, visit 6 and visit 7. Patients will be classified into 3 categories of subjects with suicidal behaviour, suicidal ideation and suicidal ideation or behaviour according to the Columbia Scoring and Data Analysis Guide (see Appendix 2). Subcategories will also be included. A subject has a suicidal ideation if she/he reports “yes” answer at any time during treatment to any one of the five suicidal ideation questions (Categories 1-5) on the C-SSRS; a suicidal behaviour if there is a “yes” answer to any one of the five suicidal behaviour questions (Categories 6-10); a suicidal ideation or behaviour is the subject has either suicidal ideation or behaviour.

The Suicidal Ideation Score corresponds to the ‘Most severe Ideation’ score reported in the eCRF and it will be presented as listings. A missing suicidal ideation score means no ideation is present. A shift table will be provided to demonstrate changes in C-SSRS categories from Baseline to Visit 6.

The BDI-II is a widely used 21-item self-report inventory measuring the severity of depression in adolescents and adults. BDI-II items are rated on a 4-point scale ranging from 0 to 3 based on the severity of each item. The maximum total score is 63. The total score derived in the eCRF will be summarized. Patients will also be classified according to the following rules: total scores of 0 to 13 indicates minimal depression, 14 to 19 indicates mild depression, 20 to 28 indicates moderate depression, and 29 to 63 indicates severe depression. A summary table will be used to describe the results at visit 1, visit 2, visit 3, visit 4, visit 5, visit 6 and visit 7. See Appendix 3 for more details on this questionnaire. A shift table will be provided to demonstrate changes in BDI-II categories from Baseline (Visit 2) to end of study (Visit 6).

The Beck Anxiety Inventory (BAI) is a widely used 21-item self-reported inventory used to assess anxiety levels in adults and adolescents. Summary tables will be used to present the total score at visit 1, visit 2, visit 3, visit 4, visit 5, visit 6 and visit 7. The total score will be computed summing up the score to each question.

The total score ranges from 0–63. The following categories for the interpretation of scores will be used: 0–7, minimal; 8–15, mild; 16–25, moderate; and 26–63, severe anxiety. A shift table will be provided to demonstrate changes in BAI categories from Baseline (Visit 2) to end of study (Visit 6).

See Appendix 4 for more details on this questionnaire.

The Pittsburgh Sleep Quality Index (PSQI) is an effective instrument used to measure the quality and patterns of sleep in adults. It differentiates “poor” from “good” sleep quality by measuring seven areas (components): subjective sleep quality (question 6), sleep latency (question 2 and 5A), sleep duration

(question 4), habitual sleep efficiency (questions 1, 3, 4), sleep disturbances (question 5B to 5J inclusive), use of sleeping medications (question 7), and daytime dysfunction over the last month (questions 8 and 9). In scoring the PSQI, seven component scores are derived, each scored 0 (no difficulty) to 3 (severe difficulty). The component scores are summed to produce a global score (range 0 to 21). Higher scores indicate worse sleep quality. The global score reported in the eCRF will be summarized at visit 1, visit 2, visit 3, visit 4, visit 5, visit 6 and visit 7. A global sum greater than “5” indicates a “poor” sleeper, therefore patients will be classified according to the global score into “good” or “poor” sleepers, a summary table will be provided to describe those results. A shift table will be provided to demonstrate changes in PSQI categories from Baseline to end of study (Visit 6). See Appendix 5 for more details on this questionnaire.

